### ***5.5 Vulnerable Populations***

Children, pregnant women, fetuses, neonates, or prisoners are not included in this research study. Educationally or economically disadvantaged persons are included but not solely targeted for recruitment. Because of our recruitment efforts for this study, it is possible that University of Pennsylvania employees and students may be invited to participate. Status of participation in the current study will be independent of the participant's work or school activities.

### ***5.6 Participant Recruitment***

[name] will oversee the study recruitment. Participants may be recruited from television, radio, internet advertisements, newspaper, flyers, transit posters, referrals, and/or from our database of previous participants who have agreed to be re-contacted for future studies. Interested participants will first complete an online RedCap screener or a telephone screen to assess their initial eligibility. Participants who are initially eligible will be screened against our registration database to confirm that they are not currently participating in another research study at our Center and have not previously reported a condition or circumstance that would make them ineligible for the current study. Those participants who remain initially eligible will then be invited to attend the lab session at our Center during which they will be presented with the IRB-approved Informed Consent Form and have their final eligibility confirmed.

## Study Procedures

### 5.7 *Eligibility Screen*

The initial pre-screening and eligibility screening will be completed via RedCap surveys. The link to RedCap survey will be shared in the recruitment materials and will be provided to any participants from previous studies who might be eligible for this study. In cases where a participant does not have access to the online screener, initial eligibility will be determined during a structured Telephone Eligibility Screen conducted by a trained member of the research team. If a participant is found to be initially eligible per the applicable inclusion and exclusion criteria, the lab session will be scheduled in order to confirm the participant's final eligibility and to complete the study questionnaires and viewing tasks. A completed telephone screen will take approximately 30 minutes.

### 5.8 *Procedures*

The lab session will occur at the Center for Interdisciplinary Research on Nicotine Addiction (CIRNA). Participants will typically receive a session reminder 24 – 48 hours prior to their scheduled session via phone call, email, and text message (if applicable).

During the session (Duration: ~2 hours), participants will complete the following:

1. Confirm the accuracy of information (i.e., name, address, phone number, email [if applicable], date of birth, age, ethnicity, race, sex assigned at birth, gender, cigarette brand type) provided during the initial Telephone Eligibility Screen. Participants will be explicitly instructed to bring in their own preferred brand of cigarettes to verify their preferred brand. If the participant does not bring in the brand of cigarettes, they reported during the Telephone Eligibility Screen, the participant may be deemed ineligible or their session may be rescheduled to a later time/day.
2. Receive and review a research study summary for potential participants. If the participant is still interested in participating in the study, they will be presented with the complete combined Informed Consent Form per below.
3. Be presented with the combined Informed Consent Form. The Informed Consent Form will be read to the participant verbatim. All of the participant's questions will be answered. Both the questions and subsequent answers will be recorded on an "ICF/HIPAA Questions Form," which will be maintained with the original Informed Consent Form. If the participant agrees to participate in the study, the Informed Consent Form will be signed (legal name) and dated by both the participant and a qualified member of the research team. Participants will receive a signed copy of the Informed Consent Form for their records.
4. Smoke a cigarette (own brand) outdoors to standardize the time to last smoke.
5. Complete baseline questionnaire:
  - Cigarette Brand Form - While viewing the participant's cigarette pack, the research staff will record the cigarette brand information on the form as appropriate. Additionally, a photocopy of the participant's cigarette packaging will be obtained for further verification of preferred brand and flavor.
  - Demographics and Sexual Orientation
  - Smoking History
  - Nicotine Dependence (FTND)
  - Pre-test measures of smoking related beliefs, attitudes towards quitting and knowledge of tobacco harms.
  - No CO measurements will be collected during the session to minimize the risk of COVID-19 infection.

6. Participants will then have their eye tracking session, completing a calibration task followed by exposure to their assigned graphic warning labels. Participants will then complete a recall task and a questionnaire with knowledge, risk beliefs and attitude measurement.
7. After viewing labels from their assigned group, each participant will perform a recognition and ranking task for all 11 labels proposed for cigarette packs by the FDA.
8. Participants will be provided compensation for their participation.

## **5.9 Description of Study Measures**

### **5.9.1 Screening and Covariates**

Age, Date of Birth (DOB), Sex Assigned at Birth, Gender, Ethnicity, and Race: Participants will report their Age, DOB, Sex Assigned at Birth, Gender, Ethnicity, and Race during the initial telephone eligibility screen. During the study session, the previously reported information will be verified in person with the participant by the research staff.

Cigarette Use Survey and Brand Form: Participants will complete a standardized survey about their cigarette use (i.e., pack type, brand, filtered or non-filtered, flavor, menthol or non-menthol, frequency, and additional information). In addition, a photocopy of the participant's cigarette pack will be obtained for further verification of brand and flavor.

Demographics, Smoking History, and Nicotine Dependence (FTND): Standard questionnaires will be administered to collect the following data: demographics, age at smoking initiation, current smoking rate, and intentions to quit. The Fagerstrom Test for Nicotine Dependence (FTND) will also be administered. The FTND is a 6-item, self-report measure of nicotine dependence derived from the Fagerstrom Tolerance Questionnaire.

### **5.9.2 Eye tracking, Recall and Knowledge (Primary Outcomes)**

Eye tracking: Participants will view the warning labels on a computer screen while wearing an eye movement tracker. The eye tracking device will provide key measure such as latency, latency duration and fixation duration for text as well as image areas of interest.

Recall: The participants will provide answers to an open-ended recall question for the text, image and/or overall message question. For the recognition task, the participants will also view all 11 label images and text statements, and would be required to identify the warning labels and text statements they saw earlier.

Knowledge: All participants will select harms caused by tobacco from a list of health issues and diseases, before as well as after viewing the warning labels on screen.

### **5.9.3 Secondary Measures**

Perceived Effectiveness Warning Label Ratings: Participants will provide subjective ratings of all the warning labels released by the FDA on measures of most and least avoidant, believable and informative.

### **5.10 Analytic Plan**

Descriptive statistics will be used to characterize the study population and smoking-related data. A factorial design will be used. The primary independent variable is warning label type (lesser-known harms vs well-known harms. Associations of independent and covariate variables with eye-tracking measures, recall, and knowledge will be assessed using unpaired t-tests or ANOVA (categorical predictors) and linear regression analysis (continuous predictors). Eye-tracking measures are continuous, and previously been observed to meet assumptions of normality. Recall is dichotomous and will be examined using logistic regression model to generate odds ratio, as in our previous work (Strasser et al., 2012; 2008). A primary outcome measure of this study is change in knowledge after exposure to graphic cigarette warning labels. This measure will be continuous when calculated on a scale and categorical when coded as increase in knowledge vs no change. Chi-square and regression analysis can be used to assess association of knowledge change with label type and by age group. Analysis will be conducted in a using Stata (Stata Corp., TX). Path analysis techniques for tobacco related mediation and moderation models will be used; covariates found to be significantly associated will be considered for inclusion in models as appropriate.

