## **3 Study Objectives**

**Aim 1:** To assess daily smokers' response to FDA PWL content on visual engagement, recall and knowledge.

H1a: Warning label images may have greater visual engagement when compared to text portions of the PWLs

H2a: The recall for image areas of PWLs might be higher post-exposure in comparison to text areas of interest.

**Aim 2: To evaluate effects of PWL risk content (lesser-known vs well-known risks) on visual engagement, recall and knowledge**

H2a: Warning labels bearing images of lesser known tobacco use harms will have longer latency and fixation durations than warning labels bearing images of well-known harms of tobacco.

H2b: The initial image/text/gist recall of PWL text and message with lesser known harms may be lower than well-known harms.

H2c: The knowledge increase will be greater among smokers exposed to warning labels highlighting lesser known harms of tobacco.

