### ***5.2 Accrual***

We have ongoing projects with current smokers who meet the criteria for the study. At the conclusion of those studies, we ask participants if we can contact them regarding future research opportunities. Further, we will post flyers and advertise online, similar to our previous recruiting efforts. We will enroll (i.e., sign an IRB-approved informed consent form) ~70 participants to . To achieve this goal, we intend to recruit 5-7 participants per month, which will allow us to enroll and randomize enough participants to complete data collection as proposed. The sample size was determined based on a previous graphic warning label eye-tracking study by Mercincavage et al.

and Lochbuehler et al. which was sufficiently powered to detect effects of a content attribute (congruency) on eye-tracking measures and image/text/message recall. In order to maximize participation in the study we will: (1) educate participants about the benefits of participation and the knowledge gained from the study; (2) schedule sessions at times convenient for participants; (3) provide reminder calls, emails, and potentially texts; and (4) provide payment for completion of the study visit and study requirements.

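### Section 5.10 codes the primary outcome, change in knowledge, in two ways without saying which answers H2c, and does not fix the pre-exposure knowledge score as a covariate

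*Combined protocol and SAP*

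**What the plan says.** H2c, in section 3, is directional and names no coding: "The knowledge increase will be greater among smokers exposed to warning labels highlighting lesser known harms of tobacco". Section 5.10 lists change in knowledge among the primary outcomes and gives it two forms: "This measure will be continuous when calculated on a scale and categorical when coded as increase in knowledge vs no change".

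Three statements in section 5.10 bear on the analysis:

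- The comparison is by arm: "The primary independent variable is warning label type (lesser-known harms vs well-known harms".
- The general rule is firm and covers knowledge: "Associations of independent and covariate variables with eye-tracking measures, recall, and knowledge will be assessed using unpaired t-tests or ANOVA (categorical predictors".
- The sentence specific to knowledge change is permissive: "Chi-square and regression analysis can be used to assess association of knowledge change with label type and by age group". It gives neither the type of regression nor its covariates.

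The last sentence of the section, which introduces path analysis, ends with the only covariate rule: "covariates found to be significantly associated will be considered for inclusion in models as appropriate".

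The pre-exposure score is in hand. The baseline questionnaire in section 5.8 includes "Pre-test measures of smoking related beliefs, attitudes towards quitting and knowledge of tobacco harms", and section 5.9.2 has all participants pick tobacco harms from a list both before and after viewing. Section 5.9.1, headed as covering screening and covariates, does not include knowledge. On sample size, section 5.2 cites earlier work "which was sufficiently powered to detect effects of a content attribute (congruency) on eye-tracking measures and image/text/message recall"; knowledge is not mentioned there.

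**The concern.** A reader of the results cannot tell from the plan which of two analyses settles H2c. The t-test wording makes the scale score the more committed reading. The later sentence still allows a chi-square test on the same outcome and predictor, and the two can disagree in the same data. As worded, the dichotomy also has no place for a participant whose score falls, which a repeated checklist permits.

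The second part is efficiency. A change score uses the pre-exposure value with its coefficient fixed at 1. A regression that estimates the coefficient is at least as precise, apart from one degree of freedom. With 70 participants and a sample size argued from other outcomes, precision that needs no further data is worth taking.

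**Working it through.** **Inputs from the documents.** 70 randomized participants (section 1), two label groups, and knowledge measured before and after exposure (sections 5.8 and 5.9.2). The figure of 70 cannot be reproduced, because no alpha, power, effect size or SD is given.

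**Inputs assumed.** Equal allocation (35 per arm), two-sided 0.05, roughly normal scores, pre/post correlation r, and k = SD pre / SD post. Ranges are shown because the documents give none of these.

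**Step 1: variance of the arm difference.** Take the post-exposure SD as 1.

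- Change score: proportional to k² + 1 − 2rk.
- Regression of post score on arm and pre score: proportional to 1 − r².
- Ratio (adjusted to change score): (1 − r²)/(k² + 1 − 2rk). With k = 1 this is (1 + r)/2.

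**Step 2: equal SDs (k = 1).** The equivalent number is 70 divided by the ratio, ignoring the lost degree of freedom. Power is at a true difference of 0.68 SD of change, where the change-score t-test has 80%.

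| r | Ratio | Equivalent number | Power, adjusted |
|---|---|---|---|
| 0.5 | 0.75 | 93 | about 90% |
| 0.7 | 0.85 | 82 | about 85% |
| 0.8 | 0.90 | 78 | about 84% |
| 0.9 | 0.95 | 74 | 81–82% |

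**Step 3: unequal SDs.**

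- k = 0.9, r = 0.7: 0.51/(0.81 + 1 − 1.26) = 0.51/0.55 = 0.927; 70/0.927 is about 75.
- k = 0.9, r = 0.8: 0.36/(0.81 + 1 − 1.44) = 0.36/0.37 = 0.973; 70/0.973 is about 72.
- k = r: the denominator is 1 − r², so the ratio is 1. There is no gain, and the lost degree of freedom costs under one point of power (simulated 80.2% against 79.4% at r = 0.8).
- k = 1.2, r = 0.7: 0.51/(1.44 + 1 − 1.68) = 0.51/0.76 = 0.67; simulated power rises from 80% to 92%.

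**Step 4: does the coding matter?** It can, but the size and even the direction depend on the score's distribution.

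- Normal change without ties, 0.68 SD: simulated chi-square power is 36–60%, against 80% for the t-test.
- Poisson count gains (means assumed 0.2 against 0.6, or 0.3 against 0.8): about 70% for chi-square against 76–81% for the t-test.
- Few participants gain, but by several items (assumed 20% against 50% gaining): 78% for chi-square against 64% for the t-test.

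**Step 5: if either coding could count.** Under the null, each test alone stays near 5% (4.2–5.5% with normal scores). Accepting whichever is significant gives 7–9% with normal change and 6–7% with count changes, so roughly 6–9%. No section states such a rule.

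**The case against.** The strongest reply is that nothing here is an error. The study is a pilot, section 2.1 calls it exploratory, it has several primary outcomes, and it sets no alpha. The change score is valid under randomization. Section 5.10 already allows regression for knowledge change, and a natural reading pairs chi-square with the categorical coding and regression with the scale. All of that stands, and it limits the point to clarity and efficiency. It does not say which result answers H2c, and allowing regression is not the same as fixing its covariate.

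Four stronger readings are tempting, and the documents do not support them:

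- **The knowledge comparison is biased.** Under randomization the change score is unbiased and its test keeps its size.
- **The study is underpowered for knowledge, or its error rate is inflated.** No power or alpha is stated, so there is no target to miss, and no section lets either coding suffice. The 6–9% figure is hypothetical.
- **Dichotomizing would cost a known, large amount of power.** Section 5.9.2 describes a checklist, which most directly yields a bounded count with ties. The 36–60% range holds only for normal change without ties; with counts the loss may be small or reversed.
- **Adjustment always gains.** The equal-SD figures hold at k = 1 only, and step 3 shows the gain vanishing at k = r.

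One further objection is right and shapes the remedy. The documents do not say how ticked items become a score. The arms see different harms, so the list that is scored determines what H2c means.

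**Conclusion.** The point holds as a gap in prespecification with an inexpensive improvement. H2c has two candidate analyses and no ranking, and a pre-exposure score collected from everyone is not committed to the model. With equal SDs, adjustment is worth between 4 and 23 extra participants on a base of 70 (74 − 70 at r = 0.9; 93 − 70 at r = 0.5). At k = 0.9 it is worth about 5 at r = 0.7 and 2 at r = 0.8. It is worth nothing at k = r, and more when the pre-exposure SD exceeds the post-exposure SD. These figures rest on assumed allocation, alpha, correlation and SD ratio; the textual gap rests on none of them. It should be fixed, but it does not threaten the study's validity.

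**What to change.** In section 5.10:

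1. Make the single primary analysis for H2c a linear regression of post-exposure knowledge score on label type, adjusted for pre-exposure knowledge score.
2. State that this covariate is fixed in advance. The significance-based clause sits in the path-analysis sentence and may not be meant for H2c, so say that it does not apply to this test.
3. Score both time points the same way, over the same list of harms in both arms, and state the scoring rule.
4. Report increase against no increase as supportive only, counting decreases as no increase.

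The cost is wording in section 5.10, including the scoring rule, and one residual degree of freedom. It needs no new data, procedures or participants.

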## 1 Study Summary

Title	PILOT: Evaluation of the new FDA warning labels: Does highlighting lesser known harms of tobacco use increase attention, recall and knowledge of tobacco harms compared to well-known harms?
Short Title	FDA Labels: Eye Tracking Study
IRB Number	843703
Methodology	
This laboratory-based study will aim to enroll 70 current cigarette users to complete a 1-day cross-sectional, randomized, parallel design protocol.
 
The participants will be randomized to one of two conditions, pictorial warning labels (PWLS) with well-known versus lesser-known tobacco harms. After completing a baseline questionnaire, the participants will view about 4 labels from the assigned group and complete a follow-up questionnaire. Eye-tracking equipment will provide data on visual processing of the warning labels and the effect of these labels on knowledge, attitudes and beliefs about smoking will be supplemented by self-report.

Study Center(s)	Single-center
Objectives	
Aim 1: To assess daily smokers' response to FDA PWL content on visual engagement, recall and knowledge
 
Aim 2: To conduct a laboratory-based study to evaluate effects of PWL risk content (lesser-known vs well-known risks) on visual engagement, recall and knowledge

Number of Participants	70 participants (randomized)

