### ***7.3 Data Processing***

The data entry screens will resemble the data collection forms as closely as possible to allow visual referencing during data entry. The data entry module will be configured for single data entry. The majority of participant data will be self-report and participants will either enter data into Qualtrics using computer, tablets or complete paper-and-pen forms during in-person visits. Some data might be collected by research staff, recorded on study-specific source documents/CRFs, and scanned in or entered directly into REDCap or MS Access. Data entry checks will be included in the entry screen designs, where appropriate, to limit the opportunity for erroneous entries due to mistyping. Such data entry checks would include value range comparisons, valid data type checks, required value checks, and/or skip pattern enforcement. Following initial telephone eligibility screening, research staff will perform subject registration.

Prior to lab session, research staff will randomize eligible participants. The randomization module will allow the research staff to randomize participants into one of the two trial arms. At the randomization attempt, the DMS will confirm milestones are accurate and that the randomization is valid. A randomization assignment will then be provided.

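### Covariates are chosen by significance and no primary model is named, so adjusted and unadjusted results compete; fix one model per outcome and adjust knowledge for its pre-test score

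*Combined protocol and SAP*

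**What the plan says.** All of the covariate handling is in section 5.10. An early sentence sets up the testing: "Associations of independent and covariate variables with eye-tracking measures, recall, and knowledge will be assessed". Label type is then compared by t-test or ANOVA for the continuous measures, by logistic regression for recall, and by chi-square or regression for change in knowledge. The last sentence of the section begins "Path analysis techniques for tobacco related mediation and moderation models will be used" and, after a semicolon, ends with the covariate rule: "covariates found to be significantly associated will be considered for inclusion in models as appropriate".

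The plan does not list the covariates, set a threshold, or say whether the association must be with the outcome, the arm or a mediator. It does not say whether an adjusted or an unadjusted estimate is the main result.

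Baseline data are plentiful. Section 5.9.1 collects "demographics, age at smoking initiation, current smoking rate, and intentions to quit", as well as the FTND. Section 5.8 adds pre-test beliefs, attitudes and knowledge. Section 5.9.2 confirms that knowledge is measured both before and after the labels are viewed. No pre-exposure measure of gaze or recall is described.

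**The concern.** In a randomised comparison the adjustment set is normally fixed in advance on prognostic grounds. Here it depends on significance tests in the same 70 people, and passing the test leads only to discretionary consideration. Two defensible analyses of each primary outcome therefore remain open once the data are visible. If the more favourable one is reported, the 5% error rate no longer holds, and this applies to each outcome separately. Section 2.1 names several primary outcomes.

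For recall there is a further problem. In logistic regression the adjusted and unadjusted odds ratios estimate different quantities even when the arms are balanced, so leaving the choice open also leaves the target of estimation undefined.

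For knowledge, the plan collects a baseline value of the outcome but does not commit to using it as a covariate. That gives up precision at almost no saving.

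**Working it through.** **Inputs.** The total is 70 randomised (section 1) in two arms: "The randomization module will allow the research staff to randomize participants into one of the two trial arms" (section 7.3). The allocation ratio, alpha, effect size and SD are not stated. I assume 1:1 allocation (35 per arm) and a two-sided 5% level. Covariate R², pre-post correlation ρ and standardised difference d are also assumptions, shown over ranges.

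**The plan's own figure.** There is no power figure to reproduce. Section 5.2 relies on earlier work described as "sufficiently powered to detect effects of a content attribute (congruency) on eye-tracking measures and image/text/message recall". Back-solving, the detectable d is (1.960 + 0.842) × √(2/35) = 0.67 at 80% power and (1.960 + 1.282) × √(2/35) = 0.77 at 90%.

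**Reach of the rule.** Read narrowly, the clause belongs to the path, mediation and moderation models that share its sentence. The main comparisons then have no stated covariate rule. Read broadly, it follows from the earlier sentence that tests covariates against eye-tracking, recall and knowledge, and it governs everything. The text does not settle which is meant.

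**Type I error if the broad reading holds.** Simulation with 35 per arm, five covariates, ordinary least squares, no arm effect and 12,000 trials per row. The Monte Carlo standard error near 5% is √(0.05 × 0.95/12,000) ≈ 0.2 points. Screening is at p < 0.05 against the outcome.

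| Joint R² | Screened model always reported | Better of unadjusted and screened | Better of unadjusted and fixed set |
|---|---|---|---|
| 0 | 4.9% | 5.2% | 6.1% |
| 0.10 | 5.2% | 6.2% | 6.8% |
| 0.20 | 4.9% | 6.8% | 7.3% |
| 0.30 | 5.2% | 7.6% | 8.1% |
| 0.50 | 5.6% | 8.6% | 8.7% |

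With 12 candidates, three of them prognostic, and R² of 0.2 to 0.3, choosing the better of unadjusted and screened gave about 6.5–8.4%. One run of 5,000 trials gave 6.2% at R² = 0.2, which is within simulation error (√(0.07 × 0.93/5,000) ≈ 0.4 points). The inflation comes from the open choice, not from the screen. The last column shows that a fixed list does not remove it either, unless one model is named as primary.

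**Knowledge: pre-test adjustment against raw change.** Power = Φ(d/(f√(2/35)) − 1.960), with f = √(2 − 2ρ) for raw change and f = √(1 − ρ²) for adjustment. At d = 0.5, d/√(2/35) = 2.092.

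| ρ | Raw change | Adjusted for pre-test |
|---|---|---|
| 0.3 | Φ(2.092/1.183 − 1.960) = 42% | Φ(2.092/0.954 − 1.960) = 59% |
| 0.5 | Φ(2.092/1.000 − 1.960) = 55% | Φ(2.092/0.866 − 1.960) = 68% |
| 0.7 | Φ(2.092/0.775 − 1.960) = 77% | Φ(2.092/0.714 − 1.960) = 83% |

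Simulation, which accounts for the lost degree of freedom, gave 41% against 58%, 54% against 65%, and 76% against 83%. Adjustment is ahead at each ρ.

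**Would a longer fixed list help the other outcomes?** Simulated power at d = 0.6 with 12 candidates, 5,000 trials per scenario:

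| Scenario | Fixed set | Screened |
|---|---|---|
| Set is exactly the three prognostic variables, R² 0.2–0.3 | 76.5–82.2% | 71.9–77.9% |
| Four-variable set holding one of them, R² 0.2 | 69.7% | 71.7% |
| Four-variable set holding one of them, R² 0.3 | 72.4% | 78.8% |
| Four-variable set holding none of them, R² 0.3 | 67.2% | 78.6% |
| No candidate prognostic | 67.1% | 67.6% |

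The sign of the difference depends on whether the right variables were chosen.

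**The case against.** A reader might infer that significance screening costs power in every model, and that each primary outcome should be adjusted for a set such as FTND, age, sex and baseline knowledge. The documents do not support this. They give no R² for any outcome, describe no baseline gaze or recall measure, and nothing in them shows that those variables predict either. The last table shows that a badly chosen list does worse than screening. In the settings where the fixed set wins, screening (71.9–77.9%) still beats the unadjusted analysis (69.1–70.6%). This objection stands, and the power argument is limited to knowledge.

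A reader might also infer that screening itself inflates type I error, or that the clause plainly governs the main comparisons. Neither holds. A screened model that is always reported stays near 5%, and the sentence structure leaves the reach open. But the narrow reading does not rescue the plan, because the label-type comparisons then have no covariate rule and still no named primary model.

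Finally, the study is titled a pilot and describes itself as exploratory, and an excess of roughly 1.5 to 3.5 percentage points is modest. That limits the severity. It does not remove the point: section 3 states directional hypotheses, several outcomes are called primary, and section 6 expects the results to be usable for regulation.

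**Conclusion.** The concern holds in a limited form. The plan leaves the choice between adjusted and unadjusted results open, at least potentially, for its primary comparisons. If the better result were reported, type I error would be about 6.5–8.4% per outcome instead of 5%, assuming joint R² of 0.2 to 0.3, 35 per arm and a two-sided 5% level. It would be about 5–6% if no covariate is prognostic. These figures come from linear models. Recall was not simulated, and the argument there is that the two odds ratios differ in meaning.

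A power gain is expected mainly for knowledge: 6 to 17 points over raw change by the formula above, at d = 0.5 and ρ from 0.7 down to 0.3. It is not established for eye-tracking or recall. This is a moderate issue for an exploratory pilot. It does not invalidate the design, but it should be corrected because wording alone can do it.

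**What to change.** For the primary label-type comparisons, replace the rule with one model per outcome, fixed before data are seen.

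- **Knowledge (continuous):** a linear model of the post-exposure score on label type, adjusted for the pre-test score regardless of its p-value. Using change as the response gives the same label-type estimate once the pre-test score is in the model. Make this primary and show the unadjusted result alongside.
- **Eye-tracking:** name a single primary model, either unadjusted or with a very short covariate set chosen in advance on prognostic grounds. Show the other as a sensitivity analysis.
- **Recall:** do the same, and state whether the reported odds ratio is adjusted or unadjusted.
- **Path, mediation and moderation models:** significance-based selection may remain here, labelled exploratory. State explicitly that the clause applies only to these models.

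The cost is analysis-plan wording and, for knowledge, one degree of freedom (residual 67 instead of 68 with 70 participants). No new data are needed.
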